20.2.2. ANALYSIS OF SECONDARY EFFICACY VARIABLES

The secondary efficacy analyses will be performed in ITT set.

The following statistical methods will be applied on the secondary efficacy endpoints:

- a) Total PFS: The estimates of the survivor function using the Kaplan-Meier approach will be displayed graphically by treatment arm. Median time and the corresponding two-sided 95% confidence interval will be presented together with the estimates for the other quartiles (SAS procedure PROC LIFETEST) by treatment arm separately.
 A Cox's proportional hazard regression model will also be performed to assess the influence of some baseline covariates on total PFS. Covariates of interest are those reported in [Paragraph 9.1](#). Hazard ratios estimates with their 95% confidence limits will be also presented (SAS procedure PROC PHREG).
- b) 3-years PFSR: The PFSR at 3 years will be estimated by the Kaplan-Meier method. The 95% confidence intervals for the PFSR will be estimated using Greenwood's estimate of the standard error (SE) and a linear transformation of the progression-free survival function.
- c) Percentage of patients alive at 2 and 3 years will be reported using Wilson score intervals for each treatment arm.
- d) BORR: Default summary statistics of the best overall response from the date of randomization to the date of objectively documented progression per RECIST version 1.1 criteria will be presented, by treatment arm.
 For each treatment arm, the Overall Response Rate (ORR) will be calculated as the percentage of patients in the ITT set who have a CR or PR before any evidence of progression (as defined by RECIST).
 A 95% confidence interval (CI) will be derived for the ORR using Wilson score intervals (CIs for a single proportion).
- e) The estimates of the survivor function of DoR using the Kaplan-Meier approach will be displayed graphically by treatment arm. Median time and the corresponding two-sided 95% confidence interval will be presented together with the estimates for the other quartiles (SAS procedure PROC LIFETEST) by treatment arm separately.
 A Cox's proportional hazard regression model will also be performed to assess the influence of some baseline covariates on DoR. Covariates of interest are those reported in [Paragraph 9.1](#). Hazard ratios estimates with their 95% confidence limits will be also presented (SAS procedure PROC PHREG).
- f) Default summary statistic of all scale scores of the EORTC QLQ-C30 and of the changes from baseline of each scale will be presented by treatment arm, according to the following scoring method.

For all the scales, the Raw Score (RS) is the mean of the component items:

$$RS = (I_1 + I_2 + \dots + I_n)/n.$$

A linear transformation to standardise the Raw Scores is used, so that scores range from 0 to 100; a higher score represents a higher (“better”) level of functioning, or a higher (“worse”) level of symptoms.

For Functional Scales, the transformation to be used is the following:

$$Score = \left\{ 1 - \frac{(RS - 1)}{range} \right\} \times 100$$

where range is the difference between the possible maximum and the minimum response to individual items.

For Symptoms scales/items and Global health status / QoL the transformation is the following:

$$Score = \left\{ \frac{(RS - 1)}{range} \right\} \times 100$$

The component items and the range which define each scale score are reported in the following table.

Table 2 Component items and range for EORTC QLQ-C30 scoring

	Scale	Number of items	Item range	Item numbers
Global health status / QoL	QL2	2	6	29,30
Functional scales				
Physical functioning	PF2	5	3	1 to 5
Role functioning	RF2	2	3	6, 7
Emotional functioning	EF	4	3	21 to 24
Cognitive functioning	CF	2	3	20, 25
Social functioning	SF	2	3	26, 27
Symptom scales / items				
Fatigue	FA	3	3	10, 12, 18
Nausea and vomiting	NV	2	3	14, 15
Pain	PA	2	3	9, 19
Dyspnoea	DY	1	3	8
Insomnia	SL	1	3	11
Appetite loss	AP	1	3	13
Constipation	CO	1	3	16
Diarrhoea	DI	1	3	17
Financial difficulties	FI	1	3	28

- g) The EQ-5D questionnaire consists of 5 5-levels items (mobility, self-care, usual activities, pain/discomfort, anxiety/depression) and of the EQ Visual Analogue Scale (EQ VAS). The digits for 5 dimensions can be combined in a 5-digit number describing the respondent’s health state (11111 indicates no problems, while 55555 indicates severe problems in all the 5 dimensions). Missing values can be coded as 9. Ambiguous values should be treated as missing values. Health states will be converted into a single index values by using the UK TTO value set. Default summary statistics and changes from baseline of the EQ-5D index will be presented by treatment arm.
- h) The following percentages will be calculated for each patient at each of the foreseen administrations. Default summary statistics and changes from baseline of these 4 scores will be presented by treatment arm.
- Percent work time missed due to health: $Q2/(Q2+Q4) \times 100$;
 - Percent impairment while working due to health: $Q5 \times 10$;

- Percent overall work impairment due to health: $\{Q2/(Q2+Q4) + [(1-(Q2/(Q2+Q4))) \times (Q5/10)]\} \times 100$
- Percent activity impairment due to health: $Q6 \times 10$.

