4.2. SAMPLE SIZE

This study was designed as a phase II, randomized trial with no formal comparative test. The sample size was discussed for the primary endpoint Overall Survival (OS).

For each arm a single-stage design as described by A'Hern (A'Hern, 2001) was used.

A median PFS of about 10 months for the combo target therapy (LGX818/MEK162) was assumed (Mc Arthur et al, 2013) and a similar value for the combo immunotherapy (ipilimumab/nivolumab) derived from the aggregate clinical activity rate of 65% (Wolchock et al, 2013) which, using an exponential distribution for PFS, could broadly give a median PFS of about 9.5 months. OS seems to be strictly correlated with total PFS.

The null hypothesis was a median OS time of 15 months (i.e. percentage of surviving patient of 33% at 24 months). The alternative hypothesis was a median OS time of 23 months (i.e. percentage of surviving of 48% at 24 months).

Using an exact 5% one-sided significance test, at least 69 patients would have to be randomized in each treatment arm when the power of the study is 80%.

For each arm the strategy would be further investigated if at least 30 patients, alive at 24 months, were observed.

Taking into account a 10% drop-out rate, a total of 230 patients would be enrolled to ensure a minimum of 207 randomized patients.

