20.1.2. ANALYSIS OF PRIMARY EFFICACY VARIABLE

The analysis will be performed in the ITT set and in the PP set.

The estimate of the survivor function using the Kaplan-Meier approach will be displayed graphically by treatment arm. Median time and the corresponding two-sided 95% confidence interval will be presented together with the estimates for the other quartiles (SAS procedure PROC LIFETEST) by treatment arm separately.

SAS-code for Kaplan-Meier approach[3]:

```
PROC LIFETEST DATA =  PLOTS=SURVIVAL(ATRISK(OUTSIDE(0.15)))
  OUTSURV= <output dataset> CONFTYPE=LOGLOG;
```

```
TIME <OS time in months>* <flag with censored data>(0)1;  

STRATA <treatment group>;  

RUN;
```

```
DATA <new dataset>;  

SET <output dataset>;  

UCL = ROUND(100*(1-SDF_UCL),.1);  

LCL = ROUND(100*(1-SDF_LCL),.1);  

RUN;
```

A Cox's proportional hazard regression model will also be performed to assess the influence of some baseline covariates on OS. Covariates of interest are those reported in section 9.1. Hazard ratios estimates with their 95% confidence limits will be also presented (SAS procedure PROC PHREG).

SAS-code for Cox's proportional hazard regression model [4,5]:

```
PROC PHREG DATA = <adam.dataset>;  

  CLASS <arm>(REF=FIRST) <gender>(REF=<'MALE'>) <melanoma type>(REF=FIRST) <stage of  

diagnosis>(REF=FIRST) <ECOG PS>(REF=FIRST) / PARAM=REF;  

  MODEL <duration of OS in months>*<censoring>(0) = <arm> <age> <gender> <melanoma type>  

<stage of diagnosis> <LDH level> <ECOG PS> / TIES=EFRON RISKLIMITS;  

RUN;
```

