20.2.1. SECONDARY EFFICACY VARIABLES & DERIVATIONS

The secondary efficacy endpoints are:

- a) Total PFS, calculated from the date of randomization until the date of the second progression (i.e., the progression to second treatment); any progression or death will be considered as an event if patient cannot complete treatment sequence.
 Any patient not known to have experienced progression or died at the time of data analysis will be censored at the time of the last recorded date on which the patient was known to be alive without disease progression.
 Total PFS (months) = [(Date of second progression or any progression/death or last contact – date of randomization +1)/30.4]
- b) 3 years PFS rate (PFSR), calculated from the date of randomization until the date of progression or death from any cause. This rate estimates the proportion of patients who did not progress and were alive 3 years after randomization.
- c) Percentage of patients alive at 2 and 3 years;
- d) Best overall response rate (BORR), defined as the best response designation, as determined by the investigator, recorded between the date of randomization and the date of objectively documented progression per RECIST version 1.1 criteria;
- e) Duration of response (DoR), calculated as the time from the date of first documented response (CR or PR) until the date of the first documented progression or death due to

¹ where 0=censored; 1 = event.

underlying cancer. If a patient with a CR or PR has no progression or death due to underlying cancer, the patient is censored at the date of last adequate tumor assessment;

DoR (months) = $[(\text{Date of first documented progression/death due to underlying cancer or date of last tumor assessment} - \text{date of first CR or PR} + 1)/30.4]$

- f) Health-related quality of life (HRQoL), by means of the 30-item European Organisation for Research and Treatment of Cancer quality of life questionnaire (EORTC QLQ-C30);
- g) General health status, by means of the European Quality of Life 5-Dimensions (EQ-5D) questionnaire;
- h) Impairment of work productivity and activity, by means of the Work Productivity and Activity Impairment: General Health (WPAI:GH) questionnaire.

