Source: XXXX.SAS, Run on DDMMYYYY

TABLE 31. Analysis of Secondary Endpoint: 3-years Progression Free Survival Rate (PFSR)

POPULATION: ITT

Statistic	Arm A (N = XX)	Arm B (N = XX)	Arm C (N = XX)
3-years PFSR [95% CI]	xx.x [xx.x;xx.x]	xx.x [xx.x;xx.x]	xx.x [xx.x;xx.x]

Notes:

The PFSR at 3 years was estimated by the Kaplan-Meier method.

The 95% CIs for the PFSR were estimated using Greenwood's estimate of the standard error and a linear transformation of the PFS function.

Source: XXXX.SAS, Run on DDMMYYYY

TABLE 32. Analysis of Secondary Endpoint: Percentage of patients alive at 2 and 3 years

POPULATION: ITT

	Statistic	Arm A (N = XX)	Arm B (N = XX)	Arm C (N = XX)
Patients alive at 2 years	n (%) [95% CI]	xxx (xx.x) [xx.x;xx.x]	xxx (xx.x) [xx.x;xx.x]	xxx (xx.x) [xx.x;xx.x]
Patients alive at 3 years	n (%) [95% CI]	xxx (xx.x) [xx.x;xx.x]	xxx (xx.x) [xx.x;xx.x]	xxx (xx.x) [xx.x;xx.x]

Notes:

The 95% CIs were calculated using Wilson Score method.

Source: XXXX.SAS, Run on DDMMYYYY

< Note for SAS Programmer: use the "binomial(Wilson)" option in FREQ procedure >

TABLE 33. Analysis of secondary endpoint: Best Overall Response (BOR) and Overall Response Rate (ORR)

POPULATION: ITT

	Statistic	Arm A (N = XX)	Arm B (N = XX)	Arm C (N = XX)
Best Overall Response (*)				
PD	n (%)	xx (xx.x%)	xx (xx.x%)	xx (xx.x%)
SD	n (%)	xx (xx.x%)	xx (xx.x%)	xx (xx.x%)
PR	n (%)	xx (xx.x%)	xx (xx.x%)	xx (xx.x%)
CR	n (%)	xx (xx.x%)	xx (xx.x%)	xx (xx.x%)
Overall Response Rate (°)	% [95% CI]	xx.x%[xx.x-xx.x]	xx.x%[xx.x-xx.x]	xx.x%[xx.x-xx.x]

Note:

Percentages are calculated relative to the total number of patients in the ITT population by treatment arm.

(*) Best overall response from the date of randomization to the date of objectively documented progression per RECIST version 1.1 criteria.

(°) Overall Response Rate is the percentage of patients with CR or PR before any evidence of progression per RECIST version 1.1 criteria. 95% CI was derived using Wilson Score interval.

Source: XXXX.SAS, Run on DDMMYYYY

TABLE 34. Analysis of Secondary Endpoint: Summary of Duration of Response (DoR)

POPULATION: ITT

		Statistic	Arm A (N = XX)	Arm B (N = XX)	Arm C (N = XX)
Duration of Response (months)	25th [95% CI]		xx.x [xx.x;xx.x]	xx.x [xx.x;xx.x]	xx.x [xx.x;xx.x]
	Median [95% CI]		xx.x [xx.x;xx.x]	xx.x [xx.x;xx.x]	xx.x [xx.x;xx.x]
	95th [95% CI]		xx.x [xx.x;xx.x]	xx.x [xx.x;xx.x]	xx.x [xx.x;xx.x]
Number of patients	Events	n (%)	xx (xx.x)	xx (xx.x)	xx (xx.x)

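### The linear-scale Greenwood interval for the 3-year PFS rate covers about 90 to 92% rather than 95% if that rate is as low as the planning medians imply; the log-log scale already used for OS avoids this

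*Supplement*

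**What the plan says.** SAP section 20.2.2 b estimates the 3-year PFS rate by Kaplan-Meier in the ITT set and specifies, for its 95% interval, Greenwood's standard error with "a linear transformation of the progression-free survival function". The note to the PFSR shell in section 26 (Table 31 in the shells, Table 29 in the list that precedes them) repeats this as "a linear transformation of the PFS function". Neither place says what happens to a limit outside 0 to 100%.

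Other intervals in the same SAP are set differently. The OS code in section 20.1.2 requests "CONFTYPE=LOGLOG". The percentages alive at 2 and 3 years and the ORR use Wilson intervals (20.2.2 c and d).

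The inputs for judging the choice are in two places. Section 4.2 sets the arm size ("at least 69 patients would have to be randomized in each treatment arm") and gives the planning PFS: "A median PFS of about 10 months for the combo target therapy (LGX818/MEK162) was assumed", and about 9.5 months for the immunotherapy combination, the latter derived with an exponential distribution. Section 20.2.1 b defines the PFS rate as "calculated from the date of randomization until the date of progression or death from any cause".

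**The concern.** A linear transformation leaves the interval symmetric on the survival scale. When only a handful of patients remain event-free, the estimate and its standard error move together: a low estimate brings a small standard error, so the interval is too short exactly when the estimate is too low. Coverage falls below nominal, the misses gather on one side, and the lower limit can drop below zero.

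Section 8.3 excludes comparative tests between the arms. For this endpoint the interval is therefore the only statement of uncertainty given for each sequence, and an upper limit that is too low understates how good a sequence might be.

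**Working it through.** **The plan's own figure.** The SAP gives no width or coverage for this interval. Its design figures do reproduce. With X binomial, n = 69 and a threshold of 30 alive at 24 months, P(X ≥ 30) is 0.0446 at 33% and 0.808 at 48%, and 207 / 0.9 = 230.

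**Step 1: the implied rate (an assumption).** With first progression or death as the event and an exponential tail, S(36) = 2^(−36/median).
- Median 10 months: 2^(−3.6) = 8.2%; 69 × 0.0825 = 5.7 patients event-free.
- Median 9.5 months: 2^(−3.789) = 7.2%; 69 × 0.0723 = 5.0 patients event-free.

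**Step 2: coverage without censoring before 36 months.** Kaplan-Meier with Greenwood then equals x/69 with the binomial Wald interval, so coverage is an exact binomial sum over the values of x whose interval contains the true rate. The log-log interval is S^exp(±1.96 v), with v = √[(1−S)/(nS)] / |ln S|; x = 0, where it does not exist, is counted as a miss.

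| | median 10 (8.2%) | median 9.5 (7.2%) |
|---|---|---|
| Linear coverage | 92.1% | 87.4% |
| Log-log coverage | 95.6% | 93.8% |
| Linear: interval wholly below the true rate | 6.9% | 11.6% |
| Linear: interval wholly above the true rate | 1.0% | 1.0% |
| Linear: lower limit negative | 16.7% | 25.0% |

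The nominal miss is 2.5% on each side. The lower limit is negative when x < 3.84 (1 − x/69) with x above 0, that is for x = 1, 2 or 3.

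Example with 3 of 69 event-free (S = 4.35%):
- Linear: 0.0435 ± 1.96 × 0.0246 = (−0.5%, 9.2%).
- Log-log: v = 0.565 / 3.136 = 0.180, which gives (1.2%, 11.0%).

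**Step 3: with censoring.** This uses Kaplan-Meier simulation, 40,000 trials per setting. Drop-out is exponential and reaches 10% by 36 months. That is an assumption: the 10% in section 4.2 only links 230 enrolled to 207 randomized.
- Linear coverage is 90.4% (median 10) and 90.6% (9.5), against 95.5% and 95.7% for log-log.
- The linear lower limit is negative in 22.7% and 31.4% of arms.
- Other patterns (30% drop-out; administrative censoring uniform over 30 to 60 or 24 to 60 months) give linear coverage of 88.9 to 91.9% and a negative limit in 22 to 45% of arms.

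**Step 4: dependence on the true rate.** Exact coverage at a fixed n is a sawtooth in the true rate, so single values mislead. Averaging the Step 2 sums over an even grid of rates, with n = 69 and no censoring:

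| True 3-year rate | Linear | Log-log |
|---|---|---|
| 6–9% | 91.5% | 95.9% |
| 10–15% | 92.8% | 95.3% |
| 15–25% | 93.6% | 95.0% |
| 25–40% | 94.2% | 95.0% |

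**Step 5: if the rate were run on total PFS.** Suppose two successive exponential phases with medians 10 and 9.5 months, so λ₁ = ln 2/10 and λ₂ = ln 2/9.5. Then S(36) = (λ₂e^(−36λ₁) − λ₁e^(−36λ₂)) / (λ₂ − λ₁) = 27.5%. At that rate linear and log-log each cover 94.0%, and negative limits essentially vanish.

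**The case against.** The strongest reply is that 7 to 8% is not a planning assumption. Section 4.2 gives approximate medians for single regimens as background to an OS design, and uses the exponential only to turn an activity rate into a median. Nothing there extends PFS to 36 months, and neither median describes Arm C, which switches treatment at 8 weeks. A plateau would raise the rate and largely remove the problem. This stands, and the size of the shortfall is conditional on it.

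The event definition is also not beyond doubt. Section 20.2.1 b omits the second-progression wording used for total PFS, so first progression is the natural reading. But Listing 52 shows the 3-year PFS flag beside a second-progression date only. On that reading the shortfall is about 1 point.

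A reader might take 87% as the headline. It is close to a trough of the sawtooth: at n = 69 without censoring, linear coverage is 94.7% for a median of 9.3 months and 86.3% for 9.4. Log-log is not better at every single rate either: at a true rate of 15% it covers 93.3% against 94.6% for linear. Its advantage is in the averages.

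A reader might also infer that the tables will often print negative limits. The SAP does not say whether limits are truncated, so this cannot be claimed. Truncation would not help coverage, because the misses are at the upper limit.

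Finally, linear Greenwood is a recognised, pre-specified method, and using other scales elsewhere is not a contradiction. No decision rule uses this endpoint; the only one is the count alive at 24 months.

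**Conclusion.** The point holds as a conditional one. With first progression or death as the event, an exponential tail from medians of about 9.5 to 10 months, and 69 patients per arm, the interval covers about 90 to 92% instead of 95%. Misses fall almost entirely where the upper limit is below the true rate, and the untruncated lower limit is negative in roughly 17 to 32% of arms (no censoring to 10% drop-out). Above a true rate of about 25% the average shortfall is under 1 point, though individual rates can do worse (93.0% at a rate of 30%).

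The documents do not support calling the method invalid or its coverage uniformly poor. This is a worthwhile, inexpensive improvement to a descriptive secondary endpoint, and it has no bearing on the primary analysis.

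**What to change.** In section 20.2.2 b and in the Table 31 note, replace the linear transformation with the complementary log-log transformation, keeping Greenwood's variance, and request it with "CONFTYPE=LOGLOG" as in the OS code of section 20.1.2. If the protocol, which was not available here, specifies the linear scale, record the change in section 4.6, which at present declares none.

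The cost is one PROC LIFETEST option and two text edits, with no change to data or design. The interval becomes asymmetric. It does not exist when the estimate is exactly zero; at the planning medians without censoring that has a chance of 0.3% (median 10) or 0.6% (9.5) per arm, so one line should say what is reported then. In that case the linear method would give the uninformative interval from 0 to 0.

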9.3. MISSING DATA

Any Missing data will not be imputed (including efficacy data).

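### Two- and three-year survival is tabulated as a crude proportion that cannot take censoring, and the 80% power of the 30-of-69 rule assumes that every patient's 24-month vital status is known.

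*Supplement*

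**What the plan says.** **Landmark survival.** SAP 20.2.2 c: "Percentage of patients alive at 2 and 3 years will be reported using Wilson score intervals for each treatment arm". The matching shell (Table 32; Table 30 in the list of tables) gives n (%) and an interval per arm in the ITT set. Its note reads "The 95% CIs were calculated using Wilson Score method", and the programmer is told to use the binomial Wilson option of PROC FREQ. Listing 51 records alive at 2 years and at 3 years as Yes or No.

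**Censoring and missing data.** SAP 20.1.1 censors OS at the last date the patient was known to be alive. SAP 9.3: "Any Missing data will not be imputed (including efficacy data". No rule classifies a patient censored alive before 24 or 36 months. SAP 11 lists loss to follow-up, and withdrawal of consent that includes follow-up, among the reasons for withdrawal.

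**Neighbouring analyses.** Item b of the same list estimates the 3-year PFS rate by Kaplan-Meier. SAP 20.1.2 and the Table 25 shell plan Kaplan-Meier OS by arm, with log-log limits at each time.

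**Design.** SAP 4.2: "For each arm a single-stage design as described by A'Hern (A'Hern, 2001) was used". The null is a "percentage of surviving patient of 33% at 24 months" and the alternative is 48%. One-sided alpha is 5%, power is 80%, and 69 patients are randomised per arm. An arm goes forward if at least 30 patients are observed alive at 24 months. On losses: "Taking into account a 10% drop-out rate, a total of 230 patients would be enrolled to ensure a minimum of 207 randomized patients". SAP 7 defines the enrolled set as all who gave consent.

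**The concern.** A Yes/No flag has no value for a patient whose follow-up ends alive at, say, month 14. Someone has to choose a code, and the SAP does not say which.

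If such patients are coded No, those who would have reached the landmark are counted as dead. If they are dropped, survivors go missing more often than deaths: a patient who dies at month 6 has to stay in follow-up for 6 months to be counted, while a survivor has to stay for 24. Both choices pull the rate down when censoring is independent of prognosis. The size depends on follow-up in each arm, so arms can differ for reasons unrelated to treatment.

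The rule in SAP 4.2 is open to the same problem because it is a fixed count of patients observed alive. A patient of unknown status cannot be in that count, and the drop-out allowance has been used up before randomisation. An unstated coding choice could then decide whether an arm reaches 30.

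**Working it through.** **Inputs from SAP 4.2.** p0 = 0.33, p1 = 0.48, n = 69 per arm, threshold 30, one-sided alpha 5%, power 80%, 230 enrolled, 207 randomised.

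**Input not in the documents.** d is the probability of being lost before 24 months, independently of survival. The range 1% to 10% is an assumption.

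**1. The plan's own figures.** With X binomial on 69 patients:
- alpha = P(X ≥ 30 | 0.33) = 4.5%
- power = P(X ≥ 30 | 0.48) = 80.8%

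A search for the smallest n that meets alpha ≤ 5% and power ≥ 80% returns n = 69 with threshold 30. The sample size is reproduced.

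**2. Where the 10% goes.** 3 × 69 = 207, and 207 / 0.9 = 230. The whole allowance lies between consent and randomisation.

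**3. Power if lost patients are not counted alive.** The chance of being observed alive at 24 months is p(1 − d), so power = P(X ≥ 30 | 69, 0.48(1 − d)) and alpha = P(X ≥ 30 | 69, 0.33(1 − d)).

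| d | expected crude rate if true rate is 48% | power | alpha |
|---|---|---|---|
| 0 | 48.0% | 80.8% | 4.5% |
| 1% | 47.5% | 78.6% | 3.9% |
| 2% | 47.0% | 76.2% | 3.4% |
| 5% | 45.6% | 68.1% | 2.3% |
| 10% | 43.2% | 52.8% | 1.0% |

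Power drops below 80% at d of about 0.4%. Some patients die before they would have been lost, so with exponential survival and loss, d = 5% and 10% mean about 3.6% and 7.1% of patients actually seen as lost.

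**4. Bias if lost patients are dropped.** Assume exponential survival and loss, true rate 48%, d = 10%:
- death rate λ = −ln(0.48)/24 = 0.03058 per month; loss rate μ = −ln(0.90)/24 = 0.00439 per month
- observed alive: A = 0.48 × 0.90 = 0.432
- observed dead: D = λ/(λ + μ) × (1 − 0.432) = 0.8745 × 0.568 = 0.497
- complete-case rate: A/(A + D) = 0.432/0.929 = 46.5%

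At d = 5% the same steps give 0.456/0.964 = 47.3%.

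**5. Power if lost patients are dropped.** This simplification takes n = 69(1 − d), rounded, and leaves the rate at 48%. With the threshold kept at 30, power is 70.4% (n = 66) and 52.6% (n = 62). With the threshold re-derived for alpha ≤ 5%, it is 78.3% (29 of 66) and 71.7% (28 of 62). The SAP provides for no re-derivation.

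**6. Kaplan-Meier comparison.** Simulation with 69 patients, exponential survival and independent exponential loss, 20,000 runs. The test is whether the one-sided 95% log-log lower limit at 24 months exceeds 33%. Power is 80.8% with no loss, 78.7% at d = 5% and 77.5% at d = 10%, with alpha about 4.2% throughout. With no loss it rejected as often as the 30-of-69 rule.

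**The case against.** **Censoring-adjusted OS is already planned.** This stands. The primary analysis is Kaplan-Meier in the ITT and PP sets, and the Table 25 shell prints the survival estimate with 95% limits over time. A reader might infer that 2- and 3-year survival will appear only in crude form. The documents do not support that. What is missing is a link from that output to Table 32 and to the rule.

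**Nothing says that Table 32 feeds the rule.** This also stands. The count of 30 appears only in SAP 4.2, and SAP 8.3 describes the results as descriptive. It is tempting to say that Table 32 decides the go rule, but that is an inference. The power argument does not need it, because it follows from the wording of the rule itself.

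**Not every lost patient is a misclassified survivor.** Correct. A patient lost at month 6 who dies at month 12 is rightly not alive at 24 months. The bias comes from lost patients who would have reached the landmark.

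**The loss may be negligible.** The documents give no rate, and SAP 11 separates withdrawal that still allows follow-up from withdrawal that does not. How vital status is traced belongs to the protocol, which is not shown here. At 1% loss the cost is about 2 points of power. The 68% and 53% are conditional figures, not forecasts.

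**The error is conservative.** True: coding losses as not alive lowers alpha. The risk is missing an active sequence, not passing an inactive one.

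**Kaplan-Meier is not a full cure.** It does not hold 80% under loss either, and it overestimates survival if patients are lost because they are deteriorating. Replacing the exact rule by an asymptotic limit would go further than the evidence requires.

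**Conclusion.** The point holds as a gap in estimation and missing-data handling, and the sample size itself is correct. Table 32 and Listing 51 use a method with no place for censored patients, while item b of the same list uses Kaplan-Meier for the same kind of quantity. Under independent censoring the reported rate is too low whichever code is chosen: at 48% true survival and 10% loss, by 4.8 points if lost patients are coded No and about 1.5 points if they are dropped.

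The stated 80% power of the 30-of-69 rule is conditional on complete 24-month status. Under the reading in which lost patients are not counted alive, 5% loss costs about 13 points and 10% about 28. These figures rest on an assumed loss rate and on independence of loss from survival. They concern 24 months only; at 3 years the issue is bias and interval validity. Because Kaplan-Meier OS is already planned and the error is conservative, this should be fixed but is not a fatal flaw.

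**What to change.** 1. In 20.2.2 c and Table 32, replace the Wilson proportion by Kaplan-Meier OS at 24 and 36 months per arm with the log-log limits already coded in 20.1.2 (TIMELIST=24 36 in PROC LIFETEST).
2. In Table 32 and Listing 51, show three states at each landmark: alive, dead, status unknown.
3. Keep the exact 30-of-69 rule. State in 4.2 that its 80% power assumes complete 24-month vital status, and that power is about 79%, 76%, 68% and 53% at losses of 1%, 2%, 5% and 10% when lost patients are not counted alive.
4. State that if any patient is censored before 24 months, the rule is read alongside the Kaplan-Meier 24-month rate and its one-sided 95% lower limit against 33%. That limit is the lower end of a two-sided 90% log-log interval.

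The cost is SAP wording, one option on an existing procedure and an amended shell and listing, with no new data. The stated power becomes less favourable, and the Kaplan-Meier estimate relies on independent censoring, which the count of unknown status lets readers judge. The wording should be settled before database lock, so that the coding of unknown status is not chosen after the results are seen.
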